4.3 Gantt Chart

* Intermediate reports will not be published publicly, and can only be consulted by participating hospitals and funding partners.

M1. Ethical Approval granted

M2. FT-IR based capsular typing test validated for 24 pneumococcal serotypes

M3. Protocol approved by all partners

M4. Preparatory phase finished, with Sensititre™ plates received, database and lab shipments completely prepared

M5. Capsular typing completed for selected non-invasive *S. pneumoniae* isolates (1995-2014)

M6. Capsular typing and MIC testing completed for all NIPD isolates collected during 20 months (2021-2022)

M7. Final statistical analyses on complete dataset finished

Publication 1 (provisional title): An FT-IR based test for fast *cps* typing in *Streptococcus pneumoniae*.

Publication 2 (provisional title): The genetic diversity of Belgian invasive and non-invasive *Streptococcus pneumoniae* strains in an international context.

Publication 3 (provisional title): Distribution of serotypes and drug resistance profiles of Belgian non-invasive *Streptococcus pneumoniae* strains in light of national vaccination campaigns

5 Microbiology

5.1 Sampling

Collecting laboratories will:

- prepare stock cultures from overnight pure cultures on blood agar plates.
- confirm *S. pneumoniae* identification by a slide agglutination test with specific antisera on the colonies, which will subsequently be transferred to a storage tube. A sufficient number of pre-filled ready-to-use tubes will be provided.
- prepare as dense suspensions as possible (preferably the culture from one blood agar plate) in 1-ml-aliquots of sterile BHI broth containing glycerol (10% v/v) in suitable screw-cap tubes, and vortexed thoroughly.
- quick freeze (e.g. in liquid nitrogen) immediately after vortexing (if part of the general lab routine), and store tubes preferably at $\leq -70^{\circ}\text{C}$.

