1.1 Pneumococcal vaccination programs reduced burden of invasive disease

Streptococcus pneumoniae is a leading cause of morbidity and mortality worldwide among children <2 years of age and in the elderly [1]. The pathogenicity of this bacteria can be divided into 2 forms: invasive (IPD) and non-invasive pneumococcal disease (NIPD). Whereas the dangerous IPD type is responsible for meningitis and bacteraemia (septicaemia), the less severe NIPD can cause upper and lower respiratory tract infections such as community acquired pneumonia (CAP) and otitis media (OM). Of note, this subdivision between IPD and NIPD pneumococcal diseases is somewhat arbitrary since a substantial proportion (10-20%) of CAP pneumonia caused by *S. pneumoniae* is associated with contemporary bacteraemia (especially in elderly and debilitated patients). The distinction between PID and NIPD relates to the laboratory diagnosis and anatomical sites from which pneumococci are isolated. In PID, *S. pneumoniae* is detected from normally sterile body fluids (blood, cerebrospinal fluid (CSF), pleural, peritoneal or articular fluids). In NIPD, pneumococcal isolates are typically isolated from superficial body sites such as ear, nose, sputum or other lower respiratory tract sites (bronchial, endotracheal aspirates, bronchoalveolar lavage,...). There are over 90 pneumococcal serotypes, classified by an immunologically distinct capsule encoded by the capsular polysaccharide (*cps*) biosynthesis locus of the genome. The capsule is a major virulence factor and the basis for the currently licensed vaccines targeted toward the paediatric and elderly communities.

In the course of the decades, various pneumococcal conjugate vaccines were successively introduced, with the 7-valent PCV7 vaccine gradually being replaced by the 10-valent PCV10 and the 13-valent PCV13 [4]. These vaccination programs have led to drastic changes in the global epidemiology of pneumococcal diseases. Spawned surveillance data unequivocally showed strong decreases in IPD rates caused by the PCV serotypes. Simultaneously, serotype replacement by non-vaccine targeted serotypes occupying nasopharyngeal niches vacated after vaccination was observed. A recent example of this is the emergence of multidrug resistant serotype 35B in IPD isolates from USA and France (**Figure 1**) [5-7].

[figure not shown]

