Figure 1. Number of serotype 35B invasive isolates by year from 1994 to 2014 in the USA, contrasting declining IPD incidence after vaccination campaigns. Figure from ref. [5].

Further, an important, and as yet underestimated, role is thought to be played by non-encapsulated pneumococcal strains (NeSP), currently not targeted by vaccination. These strains have either deleted or dysfunctional *cps* genes, or have novel genes in place at this locus [8]. NeSP strains have been isolated from patients with invasive and non-invasive pneumococcal disease, but are typically more frequently associated with non-invasive diseases like conjunctivitis (85%) and OM (8%) [9].

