- Characterization of NeSP strains by gene sequencing of the *cps* locus.
- Antibiotic susceptibility tests by microdilution (MIC).
- Whole-Genome Sequencing (WGS) for multi-drug resistance and non-typeable strains or if clonality of the same serotypes originating from different, but geographically linked, patients needs to be assessed.

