5.3 Confirmation of correct identification

All isolates will be tested for susceptibility to optochin and bile solubility. In case of doubt or negative reaction, a slide agglutination test (e.g. Slidex pneumo-Kit™, BioMérieux) as well as their MALDI-TOF (Biotyper, Bruker) profile will be examined.

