6.2 Evaluation

Our final goal is to investigate Belgian trends in serotype distribution in the non-invasive pneumococcal population. The statistical data analysis will be performed with Stat10 software (Stata Statistical Software: Release 13. College Station, TX), in collaboration with Sciensano's Epidemiology Service.

Using data from the Prospective/Retrospective surveillance track:

- Chi-square trend analysis of circulating serotypes within the non-invasive *S. pneumoniae* population, integrating retrospective data (1995-2014) with prospectively collected data (2020-2022). Data will be compared with the serotype dynamics of IPD, annually published by the NRC for pneumococcal diseases.

- Measurement of association strength within each stratum of age, gender and infection type by the prevalence ratios with exact Fisher tests for statistical significance. Particular attention will be given to NeSP isolates, their association with patient type and their influence on drug resistance.
- Chi-square trend analysis of antimicrobial resistance for all tested drug classes, in relation to historic data (1995-2013) and in association with serotype.
- Integrating metadata with WGS, we will perform phylogenetic analysis of sequenced isolates in their national and international context [13,14], and identification of genetic determinants of antibiotic resistance.

7 Access to source data and data in general

Neither of the funding partners can have a role in data collection and interpretation. However, funding partners can request at any time intermediate results or reports. The final report will be put under a six months embargo before open access publishing in Summer 2023.

8 Monitoring and quality assurance

All laboratory analyses will be performed according to ISO15089 standards. An internal project board consisting [name] (MD, PhD), [name] (Ir, PhD), [name] (Ir., PhD) and [name] (MD, PhD) will monthly follow up experimental results.

9 Adverse events

Not applicable.

10 Ethics

Upon approval of the project by at least two contact partners, a general and specific ethical application will be filed, in collaboration with Sciensano's legal department and GDPR officer. Approval of local and ethical committees will be sought.

11 Budget

PERSONNEL				
	Description	% Effort dedicated to this study	Institutional salary (3 years)	TOTAL
	Coordinating Scientist	0.6 FTE	€ 276,372	€ 165,823.2
	Statistician	0.2 FTE	-*	€ 0

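### Protocol 5.1 makes antiserum agglutination the only site confirmation test, with no provision for non-agglutinating isolates, so it risks under-counting the non-encapsulated pneumococci that 6.2 singles out

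*Protocol*

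**What the plan says.** **At the collecting laboratory.** Protocol 5.1 has the sites confirm S. pneumoniae "identification by a slide agglutination test with specific antisera on the colonies, which will subsequently be transferred to a storage tube". This is the only identification test prescribed before storage. Nothing is said about a colony that does not agglutinate.

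**At Sciensano.** Protocol 5.3 uses another order: "All isolates will be tested for susceptibility to optochin and bile solubility". Agglutination comes second: "In case of doubt or negative reaction, a slide agglutination test" is examined together with the MALDI-TOF profile.

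**On NeSP.** Section 1.1 says that serotypes are "classified by an immunologically distinct capsule encoded by the capsular polysaccharide" locus, and says of NeSP: "These strains have either deleted or dysfunctional *cps* genes, or have novel genes in place at this locus". The plan expects such strains among the study isolates. Section 4.1 lists "Characterization of NeSP strains by gene sequencing of the *cps* locus", section 5.4 sets out how they will be grouped, and section 6.2 adds: "Particular attention will be given to NeSP isolates, their association with patient type and their influence on drug resistance".

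**On eligibility.** The criteria in 4.1 require a non-invasive S. pneumoniae isolate from routine practice. They do not mention an agglutination result. The record sheet in 4.1 has no field for that result, nor for isolates that were not sent.

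**The concern.** Sections 5.1 and 5.3 apply different confirmation routes to the same isolates, and the one more likely to miss NeSP comes first. If the site antisera react with the capsule, a strain without a functional capsule locus will tend to give a negative or doubtful reaction. A laboratory told to confirm identity by this test alone may then conclude that it has no confirmed pneumococcus to store. Optochin and bile solubility do not rest on antisera, but they are run later and cannot recover an isolate that was never shipped.

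A loss of this kind would be hard to see. Each site sends its first 15 isolates of the month, so in a busy month an encapsulated isolate would take the place of a withheld NeSP. With no field for the agglutination result, the loss could be neither measured nor corrected afterwards. At stake are the NeSP prevalence in the prospective track and the associations with patient type and drug resistance named in 6.2.

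**Working it through.** The protocol gives no figure on this point to reproduce: no NeSP share for Belgium or for pneumonia, and no agglutination rate for NeSP. The check is therefore a reading of the text plus an illustration on assumed values.

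**Step 1: the sequence.** Routine isolate (4.1), then agglutination and storage at the site (5.1), then monthly transfer (4.1), then optochin and bile solubility (5.3), then capsular typing and *cps* sequencing (5.4). The only test before storage uses antisera. The tests that could confirm a non-agglutinating pneumococcus all come after shipment.

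**Step 2: NeSP prevalence.** Let *p* be the true NeSP share and *f* the fraction of NeSP lost at the site test. Both are assumptions. Then:

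observed NeSP share = *p*(1 − *f*) / (1 − *pf*)

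For *p* = 5% and *f* = 0.5: 0.025 / 0.975 = 2.6%.

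**Step 3: PCV13 share.** Section 6.1 assumes 7.5% + 7.5% + 5% + 30% = 50% PCV13 types. NeSP fall in the other half, so:

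observed PCV13 share = 0.50 / (1 − *pf*)

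For *p* = 5% and *f* = 1: 0.50 / 0.95 = 52.6%.

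| True NeSP share *p* | Fraction lost *f* | Observed NeSP share | NeSP in 2,250 shipped (no loss → with loss) | True PCV13 50% reads |
|---|---|---|---|---|
| 2% | 0.5 | 1.0% | 45 → 23 | 50.5% |
| 2% | 0.9 | 0.2% | 45 → 5 | 50.9% |
| 2% | 1 | 0 | 45 → 0 | 51.0% |
| 5% | 0.5 | 2.6% | 113 → 58 | 51.3% |
| 5% | 0.9 | 0.5% | 113 → 12 | 52.4% |
| 5% | 1 | 0 | 113 → 0 | 52.6% |
| 8% | 0.5 | 4.2% | 180 → 94 | 52.1% |
| 8% | 0.9 | 0.9% | 180 → 19 | 53.9% |
| 8% | 1 | 0 | 180 → 0 | 54.3% |

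**Step 4: scale for the PCV13 shift.** At n = 2,250 and 50%, the 95% half-width is 1.96 × √(0.25/2,250) = 2.1 points. At NeSP shares of 2% to 5%, with half or all lost, the shift is 0.5 to 2.6 points, so it is mostly within sampling error.

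**Step 5: NeSP associations.** If *f* is the same in every stratum, prevalence ratios hardly move. True shares of 5% and 2% give a ratio of 2.5. With *f* = 0.5 in both, the ratio is 2.56/1.01 = 2.5, and the cost is fewer NeSP. If *f* differs between strata, for instance because laboratories handle negatives differently, the ratio is distorted. With a true 5% in both strata but *f* = 0.5 in one and 0.9 in the other, the observed ratio is 2.56/0.52 = 4.9 where the truth is 1.

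**The case against.** The strongest reply is that 5.1 contains no rejection rule. It tells sites to confirm identity by agglutination. It does not say that a negative isolate is discarded, withheld or replaced. Eligibility is set in 4.1, where an isolate that routine practice called S. pneumoniae qualifies whatever its agglutination result. Sites are paid EUR 20 per shipped strain, which favours sending. Sections 4.1, 5.4 and 5.6 plan work on NeSP and non-typeable strains, so the authors clearly expected to receive them. This stands: a reader might infer that the plan screens NeSP out, but the text supports only a risk that they are under-counted.

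A reader might also take it as fact that NeSP fail the test. The protocol does not name the target of the antisera. That NeSP would not agglutinate is an inference from the description of serotypes and NeSP in 1.1, and it holds if the antisera are capsule-directed.

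It can further be said that NeSP are a minor part of the plan. They appear in neither the outcomes in the Summary nor the aims in section 2, and 1.1 ties them mainly to conjunctivitis, which is not a diagnosis collected under 4.1. This also stands and limits the weight of the point.

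What the reply does not remove is the mismatch. The entry test differs from the protocol's own central criteria, and the handling of a negative result is left to each of twelve laboratories.

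**Conclusion.** The point holds as a cheap improvement, with moderate confidence. Section 5.1 sets an antiserum test as the only site confirmation and makes no provision for non-agglutinating isolates, while 5.3 treats the same test as back-up. If the antisera are capsule-directed and some sites withhold negatives, NeSP prevalence in the prospective track would be too low by an unknown amount: about half the truth if half are lost. The associations in 6.2 would rest on fewer NeSP and could be biased where the loss differs between laboratories, patient groups or strains.

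Two larger conclusions are tempting but not supported. The first is that the vaccine-type result is materially inflated. At assumed NeSP shares of 2% to 5%, with half or all lost, a true PCV13 share of 50% reads 50.5% to 52.6%, and only total loss at the upper end clearly exceeds the 2.1-point half-width. The second is that the series would show a false fall in NeSP against 1995-2014. The protocol does not say how the historical isolates were identified, and 6.2 names no NeSP-specific time trend.

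**What to change.** In 5.1, bring the site confirmation into line with 5.3: accept optochin susceptibility and/or bile solubility, or the laboratory's routine identification. State that an agglutination-negative isolate otherwise identified as S. pneumoniae is still stored, shipped and counted among the 15. Add the agglutination result, where the test was done, to the record sheet in 4.1 so that the number of negatives is known.

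A sentence in 5.3 saying that a negative agglutination alone does not exclude an isolate is optional, since 5.3 already puts the other tests first.

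The cost is a sentence or two and one field on the record sheet. A few non-pneumococcal isolates may be shipped at EUR 21.50 handling each (section 11), so ten would cost EUR 215. The existing central confirmation would remove them. The change is worth making before collection starts, because isolates not stored at the site cannot be recovered.

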5.2 Storage

Isolates will be kept at $\leq -70^{\circ}\text{C}$. Cultures are stored in Brain Heart Infusion (BHI) broth containing glycerol (10% v/v). For retrieval of frozen stock cultures, the inoculum will be subcultured on sheep blood agar in 5% CO_2 .

5.3 Confirmation of correct identification

All isolates will be tested for susceptibility to optochin and bile solubility. In case of doubt or negative reaction, a slide agglutination test (e.g. Slidex pneumo-Kit™, BioMérieux) as well as their MALDI-TOF (Biotyper, Bruker) profile will be examined.

5.4 Typing of cps genes

Capsular typing is performed according to the traditional Quellung reaction. However, in this project we will investigate the use of Fourier transform infrared (FT-IR) spectroscopy to predict the serotype of the most prevalent serotypes [32,33]. It has been reported that discriminatory biochemical fingerprints, observed on FT-IR spectra, consistently correlate with sugar-based coating structures that reflect strain variation. This will allow to perform capsular typing on a medium-throughput scale (96-well plate format), at less than €5 consumable cost per sample. The test will be validated, and published, in collaboration with the NRC for pneumococcal diseases. A downside of this test is that it relies on relative (comparative) measurements, with a large number of controls (n=24) being needed in every run. This implies collaboration with the NRC to traditionally type all strains that were nontypable using FT-IR.

To type nonencapsulated strains, the *cps* locus of the strain will be sequenced to classify the strain in group I (mutation or deletion in *cps* genes) or group II (replacement of the *cps* genes) NeSP. For this last group, 2 subgroups can be distinguished in function of genes that replace the *cps* locus. In the NCC1 subgroup (null capsule clade 1), the *pspK* gene is present, while in the NCC2 subgroup the *cps* genes are replaced by *aliC* and *aliD*.

5.5 Drug susceptibility testing

The antibiotic susceptibility test will be performed by broth microdilution in cation-adjusted Mueller-Hinton broth with 2-5% (v/v) lysed horse blood, using custom-made Sensititre™ plates (Thermo Scientific, USA) containing lyophilized antibiotics. The final volume of broth in each of the wells of the microdilution plates is 50 µl, and the inoculum 5 x 10⁴ CFU. The inoculum will be prepared by direct suspension of colonies grown for 18-20 hours in 5% CO₂ on sheep blood agar in saline. Inoculum adjustment will be done with a photometric device. Incubations will be carried out at 35°C in an ambient air incubator, and MICs will be read after 20-24 hours using Vizion™ technology. The following strains will be used as first-line control: *S. pneumoniae* ATCC 49619, and *S. pneumoniae* TPN.881 (strain F9 from study 25000/BE-96-01; M phenotype).

In this surveillance study, we will test the antibiotics listed in the table below.

Antibiotic	MIC testing	
	Range (µg/ml)	No. Dilutions
Penicillin G	0.015-8	10
Amoxicillin	0.12-4	6
Moxifloxacin	0.004-8	11
Amoxicillin/Clavulanic acid 2:1	2-16	4
Cefuroxime	0.5-8	5
Cefotaxime	0.016-4	9
Clindamycin	0.016-4	9
Erythromycin	0.25-4	5
Meropenem	0.016-4	10
Levofloxacin	0.008-4	10
Tetracycline	0.25-8	6
Imipenem	0.5-4	4
Trimethoprim/Sulfmethoxazole	0.06-2	6

5.6 Whole-Genome Sequencing of selected isolates

Whole-Genome Sequencing (WGS) will be performed for multi-drug resistant and non-typeable strains or if clonality of the same serotypes originating from different, but geographically linked, patients needs to be assessed.

In this project, we budget the sequencing of 300 strains, the selection of which will be made in collaboration with the NRC for pneumococcal diseases to maximize genetic insights in the diversity of circulating IPD and NIPD serotypes.

For every selected strain, gDNA will be extracted using the automated MagCore™ platform (Atrida, NL) using standard procedures for gram-positive bacteria. Illumina MiSeq™ sequencing will be performed in-house, according to internally validated procedures. In brief, high-quality sequences are mapped onto a single reference genome, *S. pneumoniae* ATCC700669. We will use the bioinformatic pipeline designed by the NRC, to maximize the comparability with IPD isolates.

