6.1 Calculation of the sample size

To estimate the number of samples to be sent by each hospital, we calculated a total sample size based on the main objective; estimating the proportions of circulating serotypes. Based on an estimated serotype distribution of: PCV7= 7.5%, serotype 19A= 7.5%, serotype 3 =5%, 4 additional serotypes included in vaccine PCV13 =30%, serotypes not included in the vaccine non-PCV13 = 50%, we would need a total of 2250 samples to be able to obtain these estimates within 95% confidence intervals with a width of ± 20 during the whole study period (2020-2022). This translates into approximately 2 samples per week from each hospital for the 20 months period (ie total sample size/(number of hospital*weeks of study): $2250/(12*80) \cong 2$).

For the first secondary objective (establishing a statistically significant shift in serotypes from serotypes included in the PCV-13 vaccine to serotypes not included in the PCV-13 vaccine between retrospective and prospective samples), we estimated the necessary sample size to detect a 20% decrease in PCV-13 serotypes (PCV7-serotypes, 19A, 3, 4 additional PCV13) (or 20% increase in non-PCV-13 serotypes) at n=1500 for each time point (1995-2015 and 2020-2022).

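### Does the 300-genome budget in section 5.6 conflict with the rule on which strains are sequenced?

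*Protocol*

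**What the plan says.** Protocol section 5.6, headed as sequencing of selected isolates, opens with the rule that "Whole-Genome Sequencing (WGS) will be performed for multi-drug resistant and non-typeable strains". It adds a third trigger: strains of one serotype from different but geographically linked patients, when clonality has to be assessed. Section 4.1 repeats the rule for the prospective track: "Whole-Genome Sequencing (WGS) for multi-drug resistance and non-typeable strains or if clonality of the same serotypes". Neither place gives a number or a ranking.

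The second paragraph of 5.6 then says "we budget the sequencing of 300 strains, the selection of which will be made in collaboration with the NRC", the purpose being "to maximize genetic insights in the diversity of circulating IPD and NIPD serotypes". Section 11 costs exactly 300 genomes.

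On the meaning of *non-typeable*, section 5.4 has the NRC step in "to traditionally type all strains that were nontypable using FT-IR", and deals with non-encapsulated strains separately by sequencing the *cps* locus. Milestone M2 in section 4.3 is an "FT-IR based capsular typing test validated for 24 pneumococcal serotypes". Section 6.2 uses the genomes for phylogenetic analysis and for identifying genetic determinants of resistance.

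**The concern.** Two selection rules stand side by side. The first sequences every strain that meets a trigger. The second chooses 300 strains for diversity, from a pool that also includes invasive isolates. They agree only if the triggered strains fit within the slots, and no priority order, overflow rule or split between invasive and non-invasive strains is written down.

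The size of the triggered group also hangs on an unclear word. FT-IR is to be validated for 24 types, while "There are over 90 pneumococcal serotypes", and the sample-size section expects "serotypes not included in the vaccine non-PCV13 = 50" per cent. If every strain that FT-IR cannot type counts as non-typeable, the group could be large. If only strains still untyped after NRC typing count, it should be much smaller. Multidrug resistance is not defined either.

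Surveillance of emerging clones and resistance is a secondary aim. If slots ran short and diversity governed the choice, repeats of the commonest type would be dropped first. A spreading clone could then look rarer among the genomes than it is among patients.

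**Working it through.** **The plan's own figures.** Section 11: 300 × €94.50 = €28,350, as stated. Section 4.1: 12 laboratories × 15 isolates × 20 months = 3,600, as stated. The target in section 6.1 is 2,250.

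**Share covered by the budget.** 300/3,600 = 8.3%; 300/2,250 = 13.3%. If half the genomes were invasive strains (an assumption), 150/3,600 = 4.2% and 150/2,250 = 6.7%.

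**Number of triggered strains.** The Protocol gives no prevalence, so the shares below are assumed. With non-typeable share *a* and multidrug-resistant share *b*, taken as independent, the count is N × (a + b − ab). Clonality triggers are not counted.

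| a | b | a + b − ab | N = 2,250 | N = 3,600 |
|---|---|---|---|---|
| 2% | 5% | 0.069 | 155 | 248 |
| 5% | 10% | 0.145 | 326 | 522 |
| 20% | 10% | 0.280 | 630 | 1,008 |

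The first row fits within 300 and the other two do not. Nothing in the Protocol says which row is nearest the truth.

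**The broad reading of non-typeable.** Let *s* be the assumed fraction of non-PCV13 isolates outside the 24 validated types, supposing the 24 include all PCV13 types. The count is 0.5 × N × s. For s = 10%, 20% and 40% it is 113, 225 and 450 at N = 2,250, and 180, 360 and 720 at N = 3,600. The slots are used up at s = 300/1,125 = 26.7% or s = 300/1,800 = 16.7%.

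Two passages weigh against large values of *s*. Section 5.4 aims FT-IR at the most prevalent serotypes, so what falls outside should be the rarer ones. It also attaches its term expressly to FT-IR and sends those strains to be typed; a strain that comes back with a serotype is not naturally called non-typeable. Sections 4.1 and 5.6 use the word without that qualifier.

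**The possible distortion.** Take T triggered strains, a clone that is half of them, and every omission falling on that clone. Its share among the genomes is (0.5T − (T − 300))/300. For T = 360: (180 − 60)/300 = 40%. For T = 450: (225 − 150)/300 = 25%. Each figure stacks three assumptions: the size of T, the clone at 50%, and the worst possible choice of omissions.

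**Whether a planned result depends on it.** Section 6.2 plans a phylogeny and a search for resistance determinants. It names no estimate of the share of isolates in a clone or carrying a determinant. Serotype and MIC results come from all isolates sent (section 4.1), so those frequencies do not depend on who is sequenced.

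**The case for a change.** The strongest case for a change is that this is a laboratory selection rule which the Protocol itself sets, in two places, so it cannot simply be left to a statistical analysis plan. The text says triggered strains will be sequenced, while the diversity criterion reaches beyond them, and 300 is the only number given. Section 4.1 also lists non-encapsulated strains and non-typeable strains in separate bullets, so the two cannot be assumed to be the same group. A short clarification would be cheap, and without one a reader of the phylogeny may not know whether a cluster's size reflects circulation or choice.

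Much of this stands as description: the term is undefined and the priority is unwritten. It does not show a conflict. The heading of 5.6 speaks of selected isolates, 300 is a budgeted number rather than a declared cap, and the paragraphs fit together if triggers come first and diversity picks follow. The worry about a spreading clone is partly met by the third trigger, since linked repeats of one serotype are themselves a reason to sequence. Nor is the selection wholly untraceable: typing data and metadata for every non-invasive isolate go into the central database (section 5.7), and MICs are measured on all isolates sent. The fraction sequenced by serotype and resistance can therefore be worked out afterwards. Only non-random choice within such a group could not be recovered.

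A more formal scheme, with random draws within serotype and weighting, would work against the stated purpose of the 300 genomes. Purposive selection is a reasonable way to seek diversity, and a random draw could miss an unusual isolate within a common serotype or break up a linked cluster.

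**Conclusion.** No change to the plan follows. Sections 4.1 and 5.6 leave *non-typeable* and multidrug resistance undefined and do not say how the triggers relate to the 300 genomes. That is missing detail, which the laboratory and the NRC will have to settle in any case once serotypes and MICs are known. It is not a contradiction.

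The rules would pull apart only if triggered strains passed 8.3% of 3,600 isolates or 13.3% of 2,250, or lower shares if invasive strains take some of the slots. Whether they would cannot be determined from the Protocol. The worst-case fall of a clone from 50% to 40% or 25% concerns a quantity that section 6.2 does not plan to estimate.

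This conclusion rests on the genomes being used as section 6.2 describes. If clone or determinant shares were later reported as estimates for all Belgian non-invasive isolates, the way the genomes were chosen would matter and would have to be reported with them.
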